3 ANALYSIS VARIABLES

3.1 Efficacy Variables

3.1.1 Primary efficacy variable

The primary endpoint of the study is the change from Baseline of VO₂MAX at the end of Period 2. Cardio-Pulmonary Exercise Testing (CPEX) was to be performed at Screening and repeated at Baseline (Day 1), at the end of Period 1 (Week 8) and the end of Period 2 (Week 16). Details of the exercise test performed and the resultant VO₂MAX evaluations were to be reported in the CRF. For entry into the study, the patient's VO₂MAX at Screening could not exceed 75% of the predicted age-adjusted value and the VO₂MAX at Baseline (Day 1) could not be outside $\pm 20\%$ of the Screening VO₂MAX value (if the centralized CPEX assessor deems the Baseline CPEX test is not within $\pm 20\%$ of the Screening CPEX after dosing with study medication has already commenced, the subject will remain in the study and the subject's Baseline CPEX result will be taken as the valid Baseline result, unless it is deemed invalid or if the CPEX test was administered after the start of study medication).

CPEX reports were to be validated by a centralized CPEX assessor.

The VO₂MAX at the Day 1 assessment will be regarded as Baseline unless the CPEX was reported to have been assessed after the start of study medication. If this situation arises, the VO₂MAX from Screening will be regarded as Baseline. Changes and percent changes from Baseline to the end of Period 2 VO₂MAX value will be derived:

$$\text{Change at Period 2} = \text{Period 2 VO}_{2\text{MAX}} - \text{Baseline VO}_{2\text{MAX}}$$

$$\text{Percent Change at Period 2} = (\text{Period 2 VO}_{2\text{MAX}} - \text{Baseline VO}_{2\text{MAX}}) / \text{Baseline VO}_{2\text{MAX}}$$

If the patient withdraws from the study early, but provides an unscheduled or early end-of-Period 2 VO₂MAX assessment then this VO₂MAX assessment will be used in the derivation of efficacy endpoints. Only if the unscheduled or early end-of-Period 2 VO₂MAX assessment is within ± 7 days of the intended target assessment (Period 2 target = Day 113), relative to Day 1, will the derived change in VO₂MAX be used in the primary analysis using the Completer Population (see section 7.1, below).

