3.1.2 Secondary efficacy variables

Change from Baseline in VO₂MAX to end of Period 1 compared to Period 2 and Change from Baseline in VO₂MAX to end of Period 1

The change and percent change from Baseline in VO₂MAX to the end of study-drug dosing Period 1 and Period 2 will be derived:

Change at Period 1 = Period 1 VO₂MAX – Baseline VO₂MAX

Percent Change at Period 1 = (Period 1 VO₂MAX – Baseline VO₂MAX)/Baseline VO₂MAX

Change at Period 2 = Period 2 VO₂MAX – Baseline VO₂MAX

Percent Change at Period 2 = (Period 2 VO₂MAX – Baseline VO₂MAX)/Baseline VO₂MAX

As in the primary endpoint, the VO₂MAX at the Day 1 assessment will be regarded as Baseline.

In the same way as for the primary endpoint, if the patient withdraws from the study early, but provides an unscheduled or early end-of-Period 1 or end-of-Period 2 VO₂MAX assessment then this VO₂MAX assessment will be used in the derivation of efficacy endpoints. Only if the unscheduled or early end-of-Period 1 or end-of-Period 2 VO₂MAX assessment is within ±7 days of the intended target assessment (Period 1 target = Day 57; Period 2 target = Day 113), relative to Day 1, will the derived change in VO₂MAX values be used in the principal analysis of this endpoint using the Completer Population (see sections 7.2.1 and 7.2.2).

6 Minute Walk Test

A 6-minute walk test (6MWT) was to be performed at the Baseline (Day 1) assessment and repeated at the end of Period 1 (Week 8) and the end of Period 2 (Week 16).

The change and percent change from Baseline at the end of study-drug dosing Period 2 and the change and percent change from Baseline at the end of study-drug dosing Period 1 will be derived, taking the Day 1 assessment as Baseline.

If a patient withdraws from the study early, but provides an end-of-Period 1 or end-of-Period 2 assessment then this assessment will be used in the derivation of the efficacy endpoints. As in the analysis of the primary endpoint, only if the unscheduled or early end-of-Period 1 or end-of-Period 2 6MWT assessment is within ±7 days of the intended target assessment (Period 1 target = Day 57; Period 2 target = Day 113), relative to Day 1, will the derived change in 6MWT values be used in the principal analysis of this endpoint using the Completer Population (see section 7.2.3 and 7.2.4).

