7 ANALYSIS OF EFFICACY

7.1 Primary Efficacy Analysis

The primary endpoint is the change from Baseline of VO_{2MAX} at the end of Period 2. This will be analyzed using an Analysis of Covariance (ANCOVA) with covariates of baseline VO_{2MAX} and the mean plasma PEX level, with the mean taken from all available Period 2 assessments (> Week 8 to Week 16). The primary analysis population will be the Completer Population and will include an efficacy endpoint from all patients with an assessment within ± 7 days of the planned assessment. The estimated mean change in VO_{2MAX} from Baseline to Period 2 will be presented along with a 95% confidence interval of the change and the p-value. This analysis will be repeated for the percent change from Baseline of VO_{2MAX} at the end of Period 2, including the same covariates.

Descriptive statistics of the Baseline value, VO_{2MAX} at the end of Period 2 and the change and percent change from Baseline to end of Period 2 will be presented for the Completer Population.

The primary analysis and descriptive statistics table will be repeated for the MITT, and will include any imputed change in VO_{2MAX} values for patients who did not complete the study to the end of Period 2 but provided an end of Period 2 VO_{2MAX} assessment (see section 3.1.1).

Example SAS code is shown below:

```
proc mixed data=dataP2;
  class Period;
  model CHG=BASE PEXALL Period/ solution cl;
  lsmeans Period/ cl;
run;
```

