11 SAMPLE SIZE AND POWER CONSIDERATIONS

The sample size was based on a two-sided, one-sample t-test of the change from Baseline for the end of Period 2 with the following assumptions:

- Mean change from Baseline for Period 1 is 1.2mL O₂/kg/min
- Mean change from Baseline for Period 2 is 2.0mL O₂/kg/min
- Standard deviation of change from Baseline is 2.5mL O₂/kg/min for both periods
- Significance level (alpha) of 0.05

With these assumptions, a power of > 95% is anticipated for the primary outcome, and 72% for the first secondary outcome is expected for a sample size of 30 patients.

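### SAP 7.1 tests the mean of individual percent changes in VO2MAX against zero in a single arm; noise in the Baseline denominator makes that mean slightly positive even with no drug effect (minor, supportive analysis only)

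*SAP*

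**What the plan says.** The primary endpoint is the absolute change in VO2MAX from Baseline to the end of Period 2 (Protocol 8.1.1; SAP 3.1.1). SAP 3.1.1 also derives "Changes and percent changes from Baseline to the end of Period 2". The percent version is (Period 2 - Baseline)/Baseline for each patient. Baseline is the one Day 1 test, with Screening only as a fallback; the two are not averaged.

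SAP 7.1 analyses the absolute change by ANCOVA on baseline VO2MAX and mean Period 2 plasma level, reporting the estimated mean, a 95% confidence interval and a p-value. It then adds: "This analysis will be repeated for the percent change from Baseline of" VO2MAX at the end of Period 2, with the same covariates. SAP 5.1 confirms a single arm, so that p-value compares the mean with zero.

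SAP 3.1.2 derives "The change and percent change from Baseline in" VO2MAX for both periods, but SAP 7.2.1 to 7.2.5 test only absolute changes. The one tested percent change is therefore in SAP 7.1. The protocol plans no percent-change analysis, and SAP 12 does not list it among the changes from the protocol.

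**The concern.** A ratio with a noisy denominator is not centred at zero when nothing has happened. A patient who tests low by chance on Day 1 gets a large percent gain on retest. A patient who tests high by chance gets a smaller percent loss. The average is positive. In a controlled trial both arms carry this bias and it largely cancels; here nothing cancels it.

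At stake is the reading of a supportive result. The study is meant to inform a Phase 3 trial (Protocol 2.8), and a percent gain with a p-value could be read as corroborating the absolute change when part of it comes from the scale.

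**Working it through.** **Inputs from the documents (SAP 11).** "The sample size was based on a two-sided, one-sample t-test of the change from Baseline for the end of Period 2"; "Significance level (alpha) of 0.05"; SD of change 2.5 mL/kg/min; n=30; planned mean changes 2.0 (Period 2) and 1.2 (Period 1). A two-sided 0.05 test has a nominal false-improvement (upper-tail) rate of 2.5%.

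**Assumptions, not in the documents.** Baseline mean 14, 18 or 22 mL/kg/min with between-patient SD 3, 4 or 5. Share of the change variance that is Baseline test noise: 50% (equal noise at both tests, so the whole SD is test noise) or 25%.

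**Plan's own figure.** Noncentral t, df 29: a mean of 2.0 gives 98.8% power (stated >95%) and 1.2 gives 71.9% (stated 72%). Both reproduce, so the inputs are read correctly.

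**Direction.** With no effect and exchangeable tests, R = Y2/Y1 and 1/R have the same distribution. Since R + 1/R >= 2, E[R] >= 1, with equality only if there is no within-patient variation. The mean percent change is then above zero, while E[Y2 - Y1] = 0.

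**Size, first order.** Bias is about Var(Baseline error)/mean². With equal noise, Var = 2.5²/2 = 3.125. At mean 18 the bias is 3.125/324 = 0.96 points. The SE is about 100 × 2.5/18/√30 = 2.54 points, so the shift is 0.38 SE and the upper tail about 5.7%. This overstates the rate, because the ratio's SD is larger in simulation (15.7 points, against 2.5/18 = 13.9).

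**Simulation, no drug effect.** 40,000 trials of n=30 per row, additive error, no entry gate. The ANCOVA has Baseline plus a plasma-level covariate unrelated to outcome.

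| Baseline noise share | Baseline mean | Mean percent change | t-test upper / lower / total | ANCOVA upper |
|---|---|---|---|---|
| 50% | 14 | +1.96 | 5.2 / 1.1 / 6.3% | 8.9% |
| 50% | 18 | +1.18 | 4.5 / 1.3 / 5.8% | 6.8% |
| 50% | 22 | +0.77 | 3.9 / 1.5 / 5.4% | 5.5% |
| 25% | 14 | +0.97 | 3.7 / 1.6 / 5.3% | 4.9% |
| 25% | 18 | +0.56 | 3.2 / 1.9 / 5.1% | 4.1% |
| 25% | 22 | +0.36 | 3.1 / 1.8 / 4.9% | 3.8% |

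Monte Carlo error is about 0.1 point: √(0.037 × 0.963/40,000) = 0.09%. Proportional rather than additive error, with all of the SD as noise, gives a bias of +0.7 to +1.6 points; over both error types the t-test upper tail reaches about 5.4%. At a 10% noise share the bias is +0.15 to +0.35 points and the t-test upper tail 2.7 to 2.8%.

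**Comparator.** In the 50% rows the absolute change has mean 0.00 and an upper tail of 2.3 to 2.5% by t-test and 2.7 to 3.4% by ANCOVA. The rise under ANCOVA reflects its standard error, which treats Baseline as fixed. Part of the ANCOVA excess for percent change has the same source.

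**Entry gate.** Requiring Day 1 to be within 20% of Screening does not remove the bias. With additive noise, a 50% share and the gate, the mean is +0.77 to +1.22 points, with an upper tail of 4.4 to 4.5% (t-test) and 5.5 to 6.2% (ANCOVA).

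**Scale.** At mean 18 the planned effect is 2.0/18 = 11.1%, so a bias of 1.18 points is about a tenth of it.

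**The case against.** The main objection is that little depends on this. The primary endpoint and the power calculation use the absolute change, and SAP 7.1 gives the percent result no decision rule. A bias near 1 point is small beside a planned effect of about 11 and a confidence half-width of about 5. That stands, and it is why the point is minor.

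A reader might infer that the percent analysis doubles the false-positive rate. The documents do not support this. Roughly twice nominal applies to the upper tail only, and only if the whole SD of 2.5 is test noise, which no document says. The lower tail shrinks, so the total two-sided error by t-test is about 5 to 6.5%. The higher ANCOVA rates also contain the standard-error effect. Nor does the point reach the primary result, or the secondary endpoints, where no percent change is tested.

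The log ratio is also open to challenge. Zero mean log ratio is a different null from zero mean change. Because the gate selects Day 1 values and not Week 16 values, the two are not strictly exchangeable, and the mean log ratio is then about -0.3 to +0.6 points. If half of the variance is additive, mean-zero variation in response, it is about -0.4 to -1.0 points. With a baseline covariate its upper tail rises to about 2.9 to 4.2%. These limits stand and shape the fix.

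What survives is that percent change receives a formal test whose null mean is not zero, in the drug's favour, with nothing in the design to cancel it.

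**Conclusion.** The concern holds as a minor correction to one supportive analysis. The direction follows from the SAP's formula, the single Day 1 Baseline and the absence of a control arm. The size rests on an assumed Baseline mean of 14 to 22 and an assumed noise share:

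- **All of the SD is test noise:** about +0.6 to +2.0 points, with false improvement about 4 to 5.4% by t-test against 2.5%.
- **Baseline noise is 25% of the change variance:** about +0.3 to +1.0 points and 3.1 to 3.7%.
- **ANCOVA as planned:** about 3.5 to 9% over these cases, not all of it due to the ratio.

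The absolute-change primary endpoint is essentially unaffected.

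**What to change.** Change SAP 7.1 only: do not attach a confidence interval and p-value to the mean of individual percent changes. Either option would do.

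1. Keep percent change as descriptive statistics and listings, with the absolute change carrying the inference.
2. Analyse log(Period 2 VO2MAX / Baseline VO2MAX) by a one-sample t-test against zero, without the baseline covariate, and back-transform to a geometric mean percent change with 95% confidence interval. State that this is a different estimand, and that it is near-unbiased rather than exactly unbiased under the entry gate or with additive variation in response.

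The derivations in SAP 3.1.1 and 3.1.2 can stay. The cost is a short wording change and, for option 2, about one line of programming; SAP 1 allows revision before database lock. The downside of option 2 is a slightly smaller reported percent gain.

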3.1.2 Secondary efficacy variables

Change from Baseline in VO₂MAX to end of Period 1 compared to Period 2 and Change from Baseline in VO₂MAX to end of Period 1

The change and percent change from Baseline in VO₂MAX to the end of study-drug dosing Period 1 and Period 2 will be derived:

Change at Period 1 = Period 1 VO₂MAX – Baseline VO₂MAX

Percent Change at Period 1 = (Period 1 VO₂MAX – Baseline VO₂MAX)/Baseline VO₂MAX

Change at Period 2 = Period 2 VO₂MAX – Baseline VO₂MAX

Percent Change at Period 2 = (Period 2 VO₂MAX – Baseline VO₂MAX)/Baseline VO₂MAX

As in the primary endpoint, the VO₂MAX at the Day 1 assessment will be regarded as Baseline.

In the same way as for the primary endpoint, if the patient withdraws from the study early, but provides an unscheduled or early end-of-Period 1 or end-of-Period 2 VO₂MAX assessment then this VO₂MAX assessment will be used in the derivation of efficacy endpoints. Only if the unscheduled or early end-of-Period 1 or end-of-Period 2 VO₂MAX assessment is within ±7 days of the intended target assessment (Period 1 target = Day 57; Period 2 target = Day 113), relative to Day 1, will the derived change in VO₂MAX values be used in the principal analysis of this endpoint using the Completer Population (see sections 7.2.1 and 7.2.2).

6 Minute Walk Test

A 6-minute walk test (6MWT) was to be performed at the Baseline (Day 1) assessment and repeated at the end of Period 1 (Week 8) and the end of Period 2 (Week 16).

The change and percent change from Baseline at the end of study-drug dosing Period 2 and the change and percent change from Baseline at the end of study-drug dosing Period 1 will be derived, taking the Day 1 assessment as Baseline.

If a patient withdraws from the study early, but provides an end-of-Period 1 or end-of-Period 2 assessment then this assessment will be used in the derivation of the efficacy endpoints. As in the analysis of the primary endpoint, only if the unscheduled or early end-of-Period 1 or end-of-Period 2 6MWT assessment is within ±7 days of the intended target assessment (Period 1 target = Day 57; Period 2 target = Day 113), relative to Day 1, will the derived change in 6MWT values be used in the principal analysis of this endpoint using the Completer Population (see section 7.2.3 and 7.2.4).

3.2 Safety Variables

3.2.1 Adverse Events

Adverse events (AEs) were to be spontaneously reported or elicited during open-ended questioning, examination, or evaluation of a patient. The protocol (section 7.1) defines an AE as any untoward medical occurrence associated with the use of a drug in humans, whether or not considered drug related.

The following information was to be captured for all AEs:

- Start date

- End date (or ongoing status, if ongoing at the end of study)
- Outcome (Recovered/Resolved; Recovered/Resolved with Sequelae; Recovering/Resolving; Not Recovered/Not Resolved; Fatal; Unknown)
- Relationship to study treatment (Definitely Related; Probably Related; Possibly Related; Unrelated)
- Action taken with study treatment (Drug Withdrawn; Drug Interrupted; Dose Reduced; Dose Not Changed; Dose Increased; Other; Not Applicable)
- Any other action taken (No; Yes)
- Caused study discontinuation (No; Yes)
- Severity (Mild; Moderate; Severe)
- Seriousness (No; Yes)
- Adverse Device Effects (No; Yes)
- Is the event an overdose (No; Yes)
- Is the event a cancer event (No; Yes)

If the investigator deemed the AE to be serious, the reason(s) for being considered serious would be recorded in the eCRF.

AEs will be coded using the Medical Dictionary for Regulatory Activities (MedDRA).

A treatment-emergent adverse event (TEAE) is defined as any AE with a recorded start date on or after the date of the first dose of study medication. Treatment emergent (TE) status of AEs with a partial start date will be determined using available incomplete date information. For example, if the AE has a missing day field but the non-missing month and year fields place the start of the AE after the start of study medication, then the AE will be designated TE. For AEs where the available partial date information is inconclusive (for example, missing day but available month and year are equal to the month and year of start of study medication) then the AE will be classified as TE. In particular, AEs with a completely missing start date will be assumed to be TE (unless the AE stop date places the AE prior to starting treatment).

TEAEs will be split further according to whether the AE start date occurred during Period 1 or Period 2 of the Treatment Epoch, or during the Follow-up Epoch.

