4. Upon notification of a dose adjustment the site should contact the patient as soon as possible to initiate dose adjustment according to Table 1.1, below.
5. To achieve the higher target range for PEX in Period 2, the dose will initially be adjusted based on the plasma PEX level measured at Week 6 in Period 1. This dose adjustment will be performed at the Week 8 visit (start of Period 2) in accordance with the Period 2 column in Table 1.1, below. **Important:** Any change made at Week 6 will need to be accounted for when adjusting the dose at Week 8.

Table 1.1 Dose-adjustments from Week 2, Period 1 and throughout Period 2

Systemic Perhexiline Level (PEX) (ng/mL)**	Period 1 (Weeks 2 – 8) Target Range 100-300 ng/mL Start Dose of 70 mg/day, 2 tablets per day (Tablets to be taken orally in the evening) Maximum Dose 210 mg (6 tablets)	Period 2 (Weeks 9 – 16) Target Range 300-500 ng/mL Start dose will be the dose-adjustment decision based on the Period 1, Week 6 level of PEX† (Tablets to be taken orally in the evening) Maximum Dose 280 mg (8 tablets)
< 50	+2 tablets per day#	+2 tablets per day#
50 to 100	+1 tablet per day#	+2 tablets per day#
101 to 200	No change	+1 tablet per day#
201 – 300	No change	+1 tablet per day#
301 – 400	-1 tablet per day*	No change
401 – 500	-2 tablets per day*	No change
501 – 600	-3 tablets per day*	-1 tablet per day*
601 – 700	Discontinue for 1 day, and -3 tablets per day*	Discontinue for 1 day, and -2 tablets per day*

	701 - 900	Discontinue for 3 days , and -4 tablets per day*	Discontinue for 1 day , and -3 tablets per day*
	901 - 1200	Discontinue for 7 days , and -5 tablets per day*	Discontinue for 3 days , and -4 tablets per day*
	> 1200	Discontinue for 7 days , and -5 tablets per day*	Discontinue for 7 days , and -5 tablets per day*

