6.7 PERIOD 1; ADDITIONAL PROCEDURES AT COMPLETION OF WEEK 8 (DAY 57) VISIT

In addition to the procedures described above in section 6.6, the following procedures will be completed during the Period 1, Week 8 (Day 57) study visit:

- CPEX testing will be done following completion of the ECG recordings
- Body weight will be measured
- Blood samples will be obtained for routine serum chemistry safety tests and for biomarker levels of hemoglobin A1c
- The 6MWT will be done as the last procedure of the Week 8 visit

6.8 PERIOD 2: END OF TREATMENT AND AFTER COMPLETION OF WEEK 16 (DAY 113 ±3 DAYS)

Dosing should continue through the day prior to this visit. At this visit the following will be completed:

- A 12-lead ECG will be recorded in triplicate; ECGs should be taken prior to CPEX testing or blood draws and obtained after the patient has been resting comfortably in a supine position for approximately 10 minutes
- CPEX testing will be done following completion of the ECG recordings
 - If the centralized CPEX assessor deems the EOT CPEX test to be invalid, the subject may be required to return for a repeat test
- Vital signs and body weight, will be measured; heart rate and blood pressure will be measured in the seated position after 5 minutes of rest
- A blood sample will be obtained for analysis of PEX, CIS and TRANS approximately 12h after dosing on the previous study day
- Blood samples will be obtained for a complete blood cell count, routine serum chemistry safety tests and for biomarker levels of hemoglobin A1c
- Study-drug accountability will be reviewed with the patient. All remaining study-drug will be collected.
- AEs since the patient's previous site visit will be recorded. (As part of the investigation and reporting of all SAEs, every attempt will be made to obtain a blood sample for analysis of PEX, CIS and TRANS as soon as possible after awareness of an SAE.)
- ADEs will be assessed for and recorded
- Concomitant medication used since the patient's previous visit will be recorded
- A 6MWT will be done as the last procedure of the week 16 visit

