2.2 Study Design

This Phase 2, open-label, single arm study aims to confirm the optimal dosing regimen of PEX for use in a future phase 3 study. The study had planned to enroll approximately 33 patients with HCM from approximately 7-10 study sites in the US.

In the 28 days before the planned start of study dosing, each patient was to be screened for eligibility. A complete list of all eligibility criteria is available in section 4.2 and 4.3 of the study protocol.

[figure not shown]
Following screening, a patient's suitability to enter the study was to be confirmed at the Baseline assessment. Confirmation would include an evaluation of the patient's Baseline 12-lead ECG by a central assessor from ECG Corelab. Study medication was only to be dispensed after confirmation of the patient's suitability to enter the study. Any delays in the central assessment of

the Baseline ECG could result in the patient having to return to the site for study drug dispensing and having a Baseline assessment split over more than one day. The day that study drug dosing commenced was to be regarded as Day 1.

Patients who met the study inclusion and exclusion criteria were to be admitted to the study on the morning of Day 1 when they were to start their open-label, study-drug dosing regimen with PEX. The first dose of study drug was to be administered under the supervision of the study-site staff. Subsequent daily dosing throughout the dosing period of 112 days was to be done in the evening (preferably between 8-11p.m.).

CPEX was to be completed at Baseline (before the start of study-drug dosing on Day 1), and again at the end of Periods 1 and 2. After completion of study drug dosing (end of Period 2) there was to be a follow-up safety observation period before patients completed the study.

Figure 1 Outline Study Design

If a patient chose to withdraw from the study during the dosing phase, the site was to attempt to complete the following assessments:

- CPEX Testing and 6-Minute Walk Test
- vital signs and 12-Lead ECG
- Blood sample for PEX, CIS and TRANS, full blood cell count, routine safety serum chemistry tests, serum pregnancy test and serum levels of hemoglobin A1c
- Concomitant Medications and AEs
- Study drug accountability and treatment compliance

The total study duration for safety and efficacy follow-up was to be 24 weeks.

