 - ii The Baseline VO_{2MAX} was not to vary from the screening VO_{2MAX} by more than $\pm 20\%$ (with the screening test being the reference); this was to be calculated by study-site staff in order to allow a decision on patient inclusion in the study during the Baseline site-visit
- H. If the centralized CPEX assessor deemed the EOT CPEX test to be invalid, the patient may be required to return for a repeat test.
- I. Heart rate and blood pressure assessed in the seated position after 5 minutes of rest.
- J. Samples for laboratory assays were to be sent to the central lab for analysis (with the exception of the urine pregnancy test at Baseline which were to be performed locally).
- K. Females of child bearing potential. (Eligible patients were to be advised to use an adequate contraceptive method.)
- L. Serum Chemistry: sodium, potassium, bicarbonate, chloride, calcium, phosphorus, glucose, creatinine, BUN, CPK, uric acid, albumin, total protein, total bilirubin, alkaline phosphatase, ALT (SGPT), AST (SGOT), LDH, total cholesterol
- M. CBC: hemoglobin, hematocrit, RBC, MCV, MCH, MCHC, RDW, WBC count with differential (neutrophils, bands, lymphocytes, monocytes, eosinophils, basophils), platelets.
- N. Coagulation tests: prothrombin time (PT), partial thromboplastin time (PTT), and international normalized ratio (INR).
- O. CYP2D6 Poor Metabolizer status as defined by the CPIC guidelines.
- P. All determinations of systemic blood levels of PEX, CIS, and TRANS were to be measured using the PEX-CIS assay. Blood sampling for determination of PEX, CIS and AS was to be scheduled approximately 12h after dosing on the previous study day. Results for PEX and CIS were to be reported to the study sites for confirmation of a patient's phenotypic status for PEX metabolism and for dose-adjustment decisions.
- Q. Patients were to be provided with up to 4 weeks' worth of study medication at the Baseline, Week 2, 4, 6, 8, 10, 12 and 14 study visits
- R. Study-drug was to be dispensed once the ECG Corelab confirmed that the Baseline ECG met the entry criteria. The first study-drug dose was to be administered under the supervision of the study-site staff once the study-site staff confirmed that the Baseline VO_{2MAX} was within $\pm 20\%$ of the Screening CPEX.

Note:

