8.2 Adverse Events

Treatment-emergent AEs (TEAEs) occurring in patients from the Safety Population will be presented in data listings with an indication of whether the AE start date occurred during Period 1, Period 2, or the Follow-up Period. Any AEs that were recorded in the CRF from patients who were not included in the Safety Population will be listed separately and will not be included in any subsequent listings or tables.

A summary overview of TEAEs will be provided, which will present the number and percentage of patients satisfying each of the following categories. This table will be presented for Period 1 and Period 2 (see 3.2.1 for derivation) separately and for Period 1 and Period 2 combined and for the Follow-up Period, using the Safety Population.

- Any TEAEs
- Maximum severity of TEAEs
- Study drug-related TEAEs
- All TE SAEs
- All TE study drug-related TE SAEs
- TEAEs leading to death
- TEAEs leading to withdrawal of study medication

The number and percentage of patients with TEAEs will be summarized by their MedDRA preferred term within system organ class. This will be presented for Period 1 and Period 2 separately and for Period 1 and Period 2 combined and for the Follow-up Period, using the Safety Population. In this summary, any patients reporting multiple episodes of the same TEAE (i.e. same preferred term) within a single period, will be counted once. It is acknowledged that any conclusions that arise from a comparison of AEs reported during Period 1 and Period 2 may be limited due to the consecutive nature of the periods. A similar summary will be provided for study drug-related TEAEs.

The number and percentage of patients with TEAEs will be summarized by reported severity (*Severity = 'Mild', 'Moderate', 'Severe'*) within each MedDRA preferred term within system organ class. This will be presented for Period 1 and Period 2 separately and for Period 1 and Period 2 combined and for the Follow-up Period, using the Safety Population. In this summary, any patients reporting multiple episodes of the same TEAE (i.e. same preferred term) within a single period, will be counted once against the most severely reported category.

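### The date-only rule in SAP 3.2.1 counts adverse events that start before the first dose on Day 1 as Period 1 treatment-emergent events; the AE period boundaries also need stating

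*SAP*

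**What the plan says.** SAP 3.2.1 lists what is captured for each adverse event (AE). There is a start date but no start time. Two rules rest on that date. The first is "A treatment-emergent adverse event (TEAE) is defined as any AE with a recorded start date on or after the date of the first dose". The second is "TEAEs will be split further according to whether the AE start date occurred during Period 1 or Period 2 of the Treatment Epoch"; onsets in Follow-up form a third group. SAP 8.2 builds its overview on these rules: "This table will be presented for Period 1 and Period 2 (see 3.2.1 for derivation) separately", and also for the two periods combined and for Follow-up. Safety in Period 1 compared with Period 2 is a named secondary endpoint (protocol 8.1.2).

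On the order of events on Day 1, SAP 2.2 says "CPEX was to be completed at Baseline (before the start of study-drug dosing on Day 1"). Footnote R to the schedule in the same section adds "The first study-drug dose was to be administered under the supervision of the study-site staff once the study-site staff confirmed that the Baseline". The condition to be confirmed is that the Baseline VO2MAX lies within 20% of the Screening value. Under protocol 6.4 the dose is given at that visit if the ECG Corelab confirms the ECG during it. Otherwise the patient goes home without drug, and Day 1 becomes the later date on which dosing starts.

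On the Week 8 visit, item 5 of the dose-adjustment guidelines in the protocol synopsis says "This dose adjustment will be performed at the Week 8 visit (start of Period 2"). Protocol 6.7 places the same visit, Day 57, in Period 1. On the Week 16 visit, protocol 6.8 says "Dosing should continue through the day prior to this visit", and SAP 2.2 says "After completion of study drug dosing (end of Period 2) there was to be a follow-up safety observation period".

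**The concern.** Treatment-emergent status is meant to separate what happened on drug from what happened before it. Here the most strenuous pre-dose procedure, a maximal exercise test in patients with symptomatic hypertrophic cardiomyopathy, usually falls on the same calendar date as the first dose. A rule that sees only dates cannot tell the two sides of the dose apart and puts both on the drug side. An arrhythmia or syncope during that test would enter the Period 1 AE tables.

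The study is open-label with a single arm of about 33 patients, and the Period 1 versus Period 2 comparison is made within patients. A handful of misplaced events could be visible in tables of that size. Classification would also depend on how quickly the Corelab replied, which has nothing to do with the event.

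A second, smaller worry is that a programmer sent to SAP 3.2.1 for the period derivation finds no day on which Period 1 ends or Follow-up begins.

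**Working it through.** The plan states no figure on this point. The check applies the stated rules to dated events.

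**Step 1: can a pre-dose event be recorded and dated to the first-dose date?** Yes. AEs are collected from consent (protocol 6.3, 7.7.1 and 7.7.3), and the Baseline CPEX precedes dosing (SAP 2.2). Protocol 6.4 allows the first dose at the same visit. Events after the dose can share that date too: protocol 6.4 makes the six-minute walk test the last procedure of the visit, and patients are at home that evening. The date alone therefore does not give the order, and excluding all Day 1 events would also be wrong.

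**Step 2: the same event under the stated rule.** Take a syncope during the Baseline CPEX, before any drug.

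| ECG confirmation | First-dose date | AE start date | Start date on or after first-dose date? | Class |
|---|---|---|---|---|
| During the visit | Visit date | Visit date | Yes | Period 1 treatment-emergent |
| Later, dosing on a later date | After visit date | Visit date | No | Not treatment-emergent |

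**Step 3: does the SAP attend to dose order elsewhere?** It does. SAP 3.1.1 makes the choice of Baseline VO2MAX depend on whether the CPEX came after the start of medication. SAP 3.2.2 and 3.2.5 take the last laboratory or ECG value before medication as Baseline. Only the AE rule ignores order within the first-dose date.

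**Step 4: period boundaries.** Week 8 ends on Day 7 × 8 = 56, so its visit is Day 57. Week 16 ends on Day 7 × 16 = 112, so its visit is Day 113. Both match the schedule. SAP 3.2.1 gives no cut-off, so two conventions are possible.

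| Onset day | A: Period 2 from Day 57, Follow-up from Day 113 | B: visit day belongs to the period just ending |
|---|---|---|
| 56 | Period 1 | Period 1 |
| 57 | Period 2 | Period 1 |
| 58 | Period 2 | Period 2 |
| 112 | Period 2 | Period 2 |
| 113 | Follow-up | Period 2 |
| 114 | Follow-up | Follow-up |

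With visits on target, the conventions differ only for onsets on the two visit dates.

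**Step 5: which convention do the documents favour?** Mostly B:
- SAP 3.1.2 sets Day 57 as the Period 1 target and Day 113 as the Period 2 target.
- SAP 3.2.4, 3.2.5 and 3.3.1 list Week 8 under Period 1 and Week 16 under Period 2.
- The exposure categories in SAP 3.5.1 end at Day 57 for Week 8 and Day 113 for Week 16.
- SAP 7.1 takes Period 2 plasma levels from after Week 8 through Week 16.
- Protocol 4.4.3 puts the Period 2 dose change at the end of the Week 8 visit, after its assessments.

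Towards A point the start-of-Period-2 label on the Week 8 visit, the Weeks 9–16 column in protocol Table 4.1, and SAP 2.2 equating the end of dosing with the end of Period 2.

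**Step 6: size.** The dates open to question are one for treatment-emergent status (the first-dose date) and two for period (the Week 8 and Week 16 visit dates), so 1 + 2 = 3 per patient. The documents give no AE rates, so no event count follows.

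**The case against.** The Day 1 error is narrow. It needs an event to start in the pre-dose assessments and dosing to follow on the same date. Counting such events is conservative, in line with the SAP's treatment of inconclusive partial dates. Treatment-emergent status is also not attribution: the investigator rates relationship, and SAP 8.2 tabulates drug-related events separately. All of this limits the consequence and stands. It does not justify the rule, because the partial-date policy covers events whose order is unknown, whereas the site will usually know whether an event during the exercise test preceded the dose.

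SAP 5.4 places derivation specifications in stand-alone documents that are not available here, and the period boundaries may be set there. That also stands, but SAP 8.2 names SAP 3.2.1 as the place for them.

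A reader might go further and infer that events found at the Week 8 and Week 16 visits are all counted one period late, so that toxicity at 300–500 ng/mL is understated and Period 1 is inflated. The documents do not support this:
- The shift requires convention A, which the SAP does not state and most of its labels contradict.
- Assignment follows onset, not detection. A symptom reported at Week 8 that began on Day 50 stays in Period 1 under either convention.
- Laboratory and ECG results have their own summaries by period or visit (SAP 8.3 and 8.6), which do not depend on AE dates.
- Even under A the direction is not fixed. If each of the three exercise tests (Days 1, 57 and 113) produced the same number n of same-day onsets, Period 1 would gain n and lose n, and so would Period 2 and the combined total. The net change is n − n = 0 in each.

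**Conclusion.** The Day 1 point holds. For patients dosed on the date of the Baseline CPEX, SAP 3.2.1 as written makes a pre-dose onset a Period 1 treatment-emergent event, and the same onset is not one when dosing starts on a later date. This rests on the AE record having no start time or dose-order item, as the list in SAP 3.2.1 indicates. The effect is confined to one date per patient. Its size in events is unknown, and it does not by itself make an event drug-related.

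The period boundary is a secondary matter of missing detail with one inconsistent label. It affects only onsets on the Week 8 and Week 16 visit dates. No systematic shift and no direction of bias in the period comparison has been shown. The SAP's caveat in 8.2 about consecutive periods concerns interpretation and does not cover misclassification.

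**What to change.** In SAP 3.2.1:

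1. Define a treatment-emergent event as one with onset after the first dose. For AEs dated on the first-dose date, record or query whether onset was before or after that dose. Class those before as not treatment-emergent. Keep those of unknown order as treatment-emergent, in line with the SAP's existing conservative rule for inconclusive dates.
2. State the period boundaries from actual visit dates. Onsets up to and including the Week 8 visit date count in Period 1. Later onsets up to and including the Week 16 visit date count in Period 2. Follow-up starts the day after. This agrees with the SAP's own visit labels.

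The cost is a few sentences, a small change to derivation code, and one form item or a query limited to AEs dated on the first-dose date. SAP section 1 allows revision before database lock. The small downside is that an event starting late on the Week 8 visit date, after the first evening dose of Period 2, would be counted in Period 1.
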